1C	General practice recruitment study questionnaires	Will be provided to CTC and used to approach and recruit GPs and practice staff to participate in study questionnaires.
Participant Information Statements		
2A	General practice PIS	Provide a brief overview of the study and general practice requirement.
2B	Individual GP and general practice staff PIS	Provide a brief overview of the study and requirements specific to GPs and practice staff. Obtain GP and practice staff consent to participate in the study.
Participant information and Consent Forms		
3A	General practice PCF	To obtain general practice consent to participate in the study.
3B	Individual GP and general practice staff PCF	To obtain GP and practice staff consent to participate in the study.
Data Collection Tools		
4A	Clinician and general practice staff IPSBQ questionnaire pre-trial	To be completed by all participating GPs and practice staff. Will be used to collect pre-trial information from general practice staff. This survey will assess current awareness of bowel cancer screening and use of the NCSR HCP portal and behaviour change using a modified version of the IPSBQ questionnaire.
4B	Clinician and general practice staff IPSBQ questionnaire post-trial	To be completed by all participating GPs and practice staff. Will be used to collect post-trial information from general practice staff. This survey will assess current awareness of bowel cancer screening and use of the NCSR HCP portal as well as behaviour change using a modified version of the IPSBQ questionnaire.
4C	Implementation Outcomes survey mid-trial	To be completed by all participating GPs and practice staff of the intervention arm. Will be used to collect mid-trial information from general practice staff. This survey will assess implementation outcomes, including adoption and fidelity of the intervention.
4D	Implementation Outcomes survey post-trial	To be completed by all participating GPs and practice staff of the intervention arm. Will be used to collect post-trial information from general practice staff. This survey will assess implementation outcomes, including adoption and fidelity of the intervention.

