10.3.2. Secondary Outcomes

For the secondary outcomes, questionnaires have been adapted from previous Australian studies to determine these outcomes (18,31). The questionnaires will be conducted at three time points:

1. Pre: on recruitment to determine baseline awareness and existing activities
2. Mid: before the intervention is delivered to determine the potential impact of non-study activities to build awareness and/or encourage CRC screening (if they have been in field)
3. Post: on completion to determine intervention outcomes

A practice 'readiness for change' questionnaire was developed based on the Cancer Institute NSW 'Primary Care Toolkit: readiness checklist' (20). In addition to assessing 'readiness for change' the survey will determine General Practice characteristics and staff demographics. As these items are directly relevant to the trial, all practices in both the intervention and control group are required to complete the questionnaire, pre- and post- intervention delivery by a general practice representative. This questionnaire will take up to 10 minutes to complete and is available in the Appendix 4E and 4F.

Participating clinicians (GPs, nurses) and general practice staff will be invited to complete the 'Awareness and current knowledge of the NBCSP' questionnaire at baseline and trial close, adapted from the South Eastern Melbourne Primary Health Network Evaluation Report 2019 (31). The questionnaire has been adapted to include the validated Influences on Patient Safety Behaviours Questionnaire (IPSBQ) (32). The questionnaire will take up to 20 minutes to complete and is provided in full in Appendix 4A and 4B but will be available via a REDcap link.

Participating clinicians (GPs, nurses) and general practice staff in intervention practices will be invited to complete the implementation outcomes survey. This questionnaire is adapted from the validated Acceptability of Intervention Measure (AIM) scale and will assess the perceived acceptability,

appropriateness and feasibility of intervention by participants (33). The questionnaire will be available via a REDCap link at mid-trial and post-trial and will take up to 10 minutes to complete (see Appendix 4C and 4D).

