10.4. Statistical analysis and data analysis

Descriptive statistics will be used to summarise the general practice characteristics for each trial arm and the outcome results.

Intention-to-treat analysis will be used, where all general practices allocated to the trial group will be included and analysed in the group that they were assigned. Both the primary and secondary outcomes will be compared between the intervention and control groups using poisson or negative binomial regression and generalised linear modelling with an identity link function and binomial family to estimate the odds ratio and difference in proportions respectively. The regression models will use generalised estimating equations with robust standard errors to allow for clustering by general practice and will adjust for the randomisation stratification factors (e.g., practice size, state, rurality, socioeconomic indexes for areas (SEIFA) (34)). Both the relative and absolute measures of the estimated intervention effect will be reported with their respective 95% confidence intervals, and a p values calculated from the logistic regression.

The intra-practice correlation, which quantifies the proportion of the total variation in the outcome attributable to between-cluster variation in the outcome will also be estimated using mixed effects modelling and reported with 95% confidence intervals.

Results from the IPSBQ will be analysed using descriptive statistics and multivariate analysis of variance (MANOVA) to assess difference in perceived barriers pre- and post-intervention implementation. Mediation analysis will be performed to assess the degree to which changes in specific barriers influence changes in behaviour (i.e. mechanisms of action).

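### Section 10.4 specifies the IPSBQ analysis as a pre/post MANOVA naming neither trial arm nor practice, although the questionnaire is collected without arm restriction

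*Protocol*

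**What the plan says.** Section 10.4 first makes a general statement: "Both the primary and secondary outcomes will be compared between the intervention and control groups using poisson or negative binomial regression", with a binomial identity-link model for differences in proportions. Analysis is by intention to treat. On clustering it adds: "The regression models will use generalised estimating equations with robust standard errors to allow for clustering by general practice".

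The last paragraph of 10.4 then treats the IPSBQ separately, by descriptive statistics and a "multivariate analysis of variance (MANOVA) to assess difference in perceived barriers pre- and post-intervention implementation". Mediation analysis of changes in those barriers follows.

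Three instrument sets supply the secondary outcomes (Table 3, 10.3.2 and the document list in section 5):

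- **4A/4B**, awareness questionnaire containing the IPSBQ. "Participating clinicians (GPs, nurses) and general practice staff will be invited to complete the 'Awareness and current knowledge of the NBCSP' questionnaire at baseline and" again at close. No arm restriction is stated.
- **4C/4D**, implementation outcomes survey, mid- and post-trial. Here "general practice staff in intervention practices will be invited to complete the implementation outcomes survey".
- **4E/4F**, practice readiness questionnaire, one representative per practice, required in both arms, pre and post.

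On timing, 10.3.2 defines the middle time point as "Mid: before the intervention is delivered to determine the potential impact of non-study activities".

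**The concern.** For the IPSBQ the protocol fixes both a method and a contrast, and the contrast is pre versus post. A randomised control arm answers the same questionnaire at the same times, but the sentence does not use it.

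The protocol itself expects outside influences on what staff know and believe. Section 10.2 mentions incidental messaging about the screening programme, 10.2.1 says a programme review may change the information given to GPs, and 10.3.2 wants to detect non-study activities. By 10.2, baseline surveys precede six months of usual care and the post-trial survey comes at 12 months, so the pre/post contrast also spans the half-year before delivery. Any change common to both arms over that year would be read as an effect of the intervention. The mediation analysis draws on the same changes in barriers.

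Two smaller matters belong to the same secondary-outcome plan. A survey held in one arm cannot yield the between-arm comparison promised in general terms. And a survey held before delivery cannot measure uptake of what is delivered.

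**Working it through.** The protocol states no power, error rate or sample size for the secondary outcomes, so there is no figure to reproduce. The numbers below only illustrate size.

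**From the protocol:** randomisation by practice (10.5); up to 50 practices per arm and at least two GPs per practice (10.1.2).

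**Assumed, not in the protocol:** m = 2 to 8 respondents per practice; ICC of the change score 0.01 to 0.20; a change d = 0.1 to 0.3 SD (of the change score) common to both arms; one score standing in for the multivariate test; pre and post answers paired.

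**1. Change common to both arms, zero intervention effect.** With n respondents treated as independent,

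P(significant) = Φ(d√n − 1.96) + Φ(−d√n − 1.96).

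Example: d = 0.2 and n = 50 × 2 = 100 give d√n = 2.0, and Φ(0.04) = 0.516 (the second term is negligible).

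| m | d | intervention arm only (n = 50m) | both arms pooled (n = 100m) |
|---|---|---|---|
| 2 | 0.1 | 0.17 | 0.29 |
| 2 | 0.2 | 0.52 | 0.81 |
| 2 | 0.3 | 0.85 | 0.99 |
| 5 | 0.1 | 0.35 | 0.61 |
| 5 | 0.2 | 0.89 | 0.99 |
| 5 | 0.3 | 1.00 | 1.00 |

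**2. The same setting simulated with clustering** (50 practices per arm, 4,000 runs, no intervention effect; share of runs significant):

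| m | ICC | d | pooled pre/post test | between-arm test on practice means |
|---|---|---|---|---|
| 5 | 0.10 | 0 | 10.4% | 5.2% |
| 5 | 0.10 | 0.2 | 98.4% | 5.1% |
| 2 | 0.05 | 0.2 | 79.5% | 4.7% |

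The between-arm test holds its level because the common change cancels.

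**3. Clustering alone.** Design effect DE = 1 + (m − 1) × ICC. Actual level of a nominal two-sided 5% test that ignores it = 2 × [1 − Φ(1.96/√DE)]. Example: m = 8, ICC 0.20 gives DE = 1 + 7 × 0.20 = 2.40, 1.96/√2.40 = 1.265, level 20.6%.

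| m | ICC 0.01 | 0.05 | 0.10 | 0.20 |
|---|---|---|---|---|
| 2 | 5.1% | 5.6% | 6.2% | 7.4% |
| 5 | 5.5% | 7.4% | 9.8% | 14.4% |
| 8 | 5.8% | 9.2% | 13.3% | 20.6% |

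**4. Does the general GEE sentence already cover the IPSBQ?** It promises a between-arm, cluster-adjusted comparison, but its outcome models are Poisson or negative binomial and binomial. Choosing MANOVA implies that the IPSBQ barrier scores are treated as continuous, and those families do not suit such scores. Section 10.4 therefore holds two plans for one instrument: one with the right contrast and an unsuitable model, the other with a model for continuous scores and the wrong contrast.

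**5. One-arm surveys.** Table 3 lists 4C, 4D, 4E and 4F for the implementation outcome, which 8.2 defines as adoption. Adoption is described only for 4C/4D ("This survey will assess implementation outcomes, including adoption and fidelity of the intervention"), which have no control group. 4E/4F cover both arms, but section 5 and 10.3.2 describe them as measuring readiness for change and practice characteristics.

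**6. Mid time point.** Section 10.3.2 puts it before delivery, to pick up non-study activity. Section 10.2 puts a mid-trial implementation survey with or after delivery, in intervention sites. Section 5 says 4C measures adoption and fidelity. A survey before delivery could not do that, and a survey in the intervention arm alone could not separate non-study activity from trial support.

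**The case against.** The strongest reply is that 10.4 already plans a randomised comparison. Primary and secondary outcomes are to be compared between arms by intention to treat, with GEE and robust standard errors, and 4A/4B and 4E/4F supply data from both arms. This stands. A reader might infer that the secondary outcomes have no valid randomised comparison at all; the protocol does not support that.

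Second, the MANOVA sentence is silent on arm and practice rather than excluding them. A MANOVA can carry a group factor and repeated measures, and a SAP that is not shown may add them. This stands in part. It would be wrong to say that the plan treats one person's two answers as independent, for nothing in the text says so. But the contrast itself is stated, and it is time.

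Third, the MANOVA may be meant as a mechanism analysis beside the secondary-outcome comparison, since 8.2 names awareness and understanding as the service outcome and mediation follows directly. That is possible, and the protocol does not settle it. A mechanism analysis would still need the control arm to separate the intervention's effect on barriers from background change. The awareness items may be binary or counts, so the objection to the count and binomial models is limited to the IPSBQ scores.

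Fourth, only those who received the intervention can judge its acceptability, appropriateness and feasibility. This is right: giving 4C/4D in one arm is sensible, and the fault is only that the general between-arm sentence makes no exception for them.

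Fifth, error rates of 7% to 21% from clustering could be quoted, but they assume four to eight respondents per practice and ICCs of 0.05 to 0.20. The only staffing figure in the protocol is two GPs, where inflation is small.

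**Conclusion.** The point holds for the IPSBQ sentence. As written, it tests change over time without naming arm or practice, out of line with the between-arm, cluster-adjusted plan in the same section.

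The missing arm contrast is the main matter. Under an assumed common change of 0.2 SD and no intervention effect, a pre/post test would be significant in about half to nearly all trials (0.52 to 0.99), depending on respondents per practice and on whether one arm or both are used. The bias equals the whole common change, whatever its size; the protocol gives no figure for it.

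Clustering is secondary: about 5% to 7% at two respondents per practice, up to about 21% at eight with an ICC of 0.20, all on assumed ICCs. If the analysis also left the pre/post pairing unused, that would normally pull the other way, so the net error rate cannot be predicted from the text.

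Two narrower points also stand: 4C/4D cannot support the between-arm statement, and the mid-survey time point is contradictory. The co-primary outcomes are not affected. The change should be made, but it is a correction to secondary analyses.

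**What to change.** - **IPSBQ.** Make the result for each domain score the between-arm difference in post score, adjusted for baseline score and state (the stratification factor in 10.5). Handle clustering with a linear GEE and robust standard errors by practice, in keeping with the other models, or a linear mixed model with a practice random intercept. Keep the pre/post MANOVA as descriptive only.
- **General model sentence.** Say that the count and binomial models do not apply to the IPSBQ domain scores.
- **4C/4D.** State that they are descriptive in the intervention arm and exempt from the between-arm statement.
- **4E/4F.** Label any between-arm comparison as readiness. It should not stand in for adoption, which these questionnaires are not described as measuring.
- **Mid survey.** Reconcile 10.3.2, 10.2 and the section 5 entry for 4C, so that one time point and one purpose are stated.

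The cost is protocol and SAP wording. No new data are needed: 4A/4B are already planned at both time points without arm restriction, and 11.1.2 links each person's questionnaire data to a study number, which allows baseline adjustment.

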10.8. Schedule of events

Table 5 Pilot trial schedule of events

TIME POINT**	STUDY PERIOD								
	Enrolment		Allocation	Post-allocation					Close-out
	Aug 2023	Sep 2023	Nov 2023	Jan 2024	March 2024	May 2024	July 2024	Sep 2024	Oct 2024
Visit window	+/- 30 days	+60 days	+/- 14 days	+/- 60 days	+/- 14 days	+/- 14 days	+/- 14 days	+/- 30 days	+/- 30 days
PHN Research Agreement	X								
Recruitment of CTCs	X								
ENROLMENT:									
Eligibility screen		X							
Informed consent		X							
Randomisation / Allocation			X						
INTERVENTIONS:									
Preparation of intervention			X	X					
Delivery of intervention					X				
Ongoing support from CTC (Intervention arm)					X	X	X	X	
Monitoring from CTC (Control arm)					X	X	X	X	
ASSESSMENTS:									
Baseline data collection		X	X						
clinical audit (primary outcome)		X	X	X					
Baseline surveys (secondary outcome)				X	X	X	X	X	
Ongoing data collection (secondary outcomes)									
Post-intervention data collection clinical audit (primary outcome)									X
Post-intervention surveys (secondary outcome)									X

Note: Pilot trial schedule of events: Study specific adapted from The University of Sydney Clinical Trials Study Protocol template.

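### The mediation analysis is worded as a mechanism, but barriers are scheduled only at baseline and trial close, so the direction between barriers and behaviour cannot be established

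*Protocol*

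**What the plan says.** Protocol section 10.4 plans two analyses of the IPSBQ. A MANOVA is to be used "to assess difference in perceived barriers pre- and post-intervention implementation". A mediation analysis follows: "Mediation analysis will be performed to assess the degree to which changes in specific barriers influence changes in behaviour (i.e. mechanisms of action". The second sentence is directional: barriers are the mediator, behaviour is the outcome, and the result is to be read as how the intervention works.

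The schedule for the mediator is in section 10.3.2. The awareness questionnaire is described thus: "The questionnaire has been adapted to include the validated Influences on Patient Safety Behaviours Questionnaire (IPSBQ". It is offered as a "questionnaire at baseline and trial close". The list of study documents (section 5) has a pre-trial form, 4A, and a second form, 4B, titled "Clinician and general practice staff IPSBQ questionnaire post-trial". It lists no mid-trial version. Table 3 (section 10.3) gives pre and post as the time points for 4A and 4B.

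The behaviour side runs as follows. Delivery is March to August 2024 (section 4, study duration). Recommendations and completed tests are tracked over 12 months (Table 3). Section 10.2 puts the post-trial audit and the post-trial surveys together at 12 months. Table 5 (section 10.8) has a row for "Post-intervention surveys (secondary outcome" surveys, marked at the October 2024 close-out.

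**The concern.** A mediation analysis needs the mediator to be measured before the outcome it is said to affect. Here the only barrier score after baseline is taken when the behaviour period is ending or over. Staff who have spent months recommending screening may report fewer barriers because of that experience. The planned analysis would count this reverse effect as mediation, and section 10.4 would have it reported as a mechanism.

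What is at stake is the interpretation of one secondary, explanatory analysis. The measurement schedule is fixed in the protocol. A statistical analysis plan could define behaviour or choose an estimator, but it could not supply a barrier measurement that was never taken.

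**Working it through.** The protocol gives no figure for the mediation analysis, so there is none to reproduce. The check has two parts: the timing, and an illustration of what the timing permits.

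**Timing**

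| Item | When | Where stated |
|---|---|---|
| IPSBQ, form 4A | Baseline | Sections 5, 10.3.2; Table 3 |
| Delivery of intervention | March to August 2024 | Section 4 |
| Recommendations and tests | Tracked over 12 months | Table 3 |
| Post-trial audit | 12 months | Section 10.2 |
| IPSBQ, form 4B | Trial close, with the audit | Sections 5, 10.2, 10.3.2; Table 3 |

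The number of IPSBQ administrations specified between the start of delivery and the end of the behaviour window is zero.

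Section 10.4 does not say what behaviour is, so both readings were checked:
- If it is recommendations or tests, the follow-up barrier score comes at the end of the period over which they accrued.
- If it is the behaviour-change content that section 5 attributes to 4A and 4B, mediator and outcome come from one form at one time.

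On neither reading does the mediator precede the outcome.

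**Size in an assumed worst case**

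Let X be arm, Y behaviour and M reported barriers. Assume that arm changes behaviour, that behaviour changes reported barriers, and that barriers do nothing to behaviour:
- Y = aX + e, with var(e) = 1
- M = cY + u, with var(u) = 1 − c², so var(M given X) = c² + 1 − c² = 1

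The true mediated effect is 0. The product-of-coefficients method nevertheless finds:
- arm to M: a × c
- M to Y, adjusted for arm: cov(Y, M given X) / var(M given X) = c / 1 = c
- apparent indirect effect: a × c × c = a·c²
- apparent share of the total effect: a·c² / a = c²

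Here c is the arm-adjusted correlation r between close-out barriers and behaviour. The share is 0.3² = 9%, 0.5² = 25% or 0.7² = 49%.

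A simulation of the same model used 100 practices allocated 1:1, one score per practice, 4,000 replicates, and joint significance of the two paths at two-sided 5%. It gave shares of about 9%, 25% and 49%, and declared mediation this often:

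| Assumed arm effect on behaviour | r = 0.3 | r = 0.5 | r = 0.7 |
|---|---|---|---|
| 0.5 SD | 10% | 24% | 42% |
| 0.8 SD | 18% | 52% | 80% |

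The arm effects and correlations are assumptions; none is in the protocol.

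**Would an extra wave during delivery cure it?**

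Only with the right adjustment. Split behaviour into Y1 (March to the wave) and Y2 (after the wave), with the same arm effect a and arm-adjusted correlation ρ. Let M at the wave depend on Y1 only. Then cov(Y2, M given X) = cρ, the apparent indirect effect is a·c × cρ, and the share is c²ρ.
- ρ = 0.8: 0.09 × 0.8 = 7.2%; 0.25 × 0.8 = 20%; 0.49 × 0.8 = 39.2%
- ρ = 0.5: 4.5%; 12.5%; 24.5%

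Adjusting for baseline alone therefore leaves half or more of the false share at these values. If Y1 is also in the model, M carries no further information on Y2 under these assumptions, and the false share is 0.

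**The case against.** Three passages could suggest that barriers are measured during delivery.
- Section 10.3.2 says in general terms that the questionnaires have three time points. It defines the middle one as "Mid: before the intervention is delivered to determine the potential impact of non-study activities", so that point could not record a change produced by delivery. The same section limits the questionnaire carrying the IPSBQ to baseline and close.
- Section 5 lists an "Implementation Outcomes survey mid-trial" (form 4C). It is a different instrument and goes to the intervention arm only.
- Table 5 has a row for ongoing collection of secondary outcomes. Its marks appear displaced in the text as read, so nothing is rested on them. The row names no IPSBQ administration, and the texts specific to that instrument give pre and post only.

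Some stronger readings should be resisted.
- A reader might infer that barriers are measured strictly after behaviour. With behaviour undefined, and changes being related to changes over the same interval, the documents support only that the mediator is not shown to come first.
- A reader might infer that the data say nothing about mechanism. Randomisation still supports the arm effect on barriers and the arm effect on behaviour. What is unsupported is the direction of the path between them. That path is not randomised under any schedule, so better timing would not by itself prove a mechanism.
- A reader might infer that a false mechanism would pass into the scale-up plan. Sections 10.12 and 15 say that trial results contribute to that plan and to a predictive model. Neither mentions the mediation analysis.

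**Conclusion.** The point holds as one about interpretation. Followed as written, section 10.4 would report a directional mechanism that the protocol's own schedule cannot support, because barriers changing behaviour and behaviour changing reported barriers would look the same in these data.

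The timing result rests on the protocol text alone. The 9%, 25% and 49% shares rest on assumed correlations and on all the association being reverse. They are a worst case and not an expected bias. The false-positive rates also rest on assumed arm effects and on one score per practice.

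This affects a secondary explanatory analysis. The co-primary comparisons of recommendations and completed tests do not depend on it.

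**What to change.** **Main change, wording only.** In section 10.4, delete the verb *influence* and the bracketed reference to mechanisms of action. Suggested text: *An exploratory analysis will describe the association between pre-post change in perceived barriers and change in behaviour; no direction of effect will be inferred.* The same sentence should say which measure of behaviour is used. The cost is a short protocol amendment.

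**Optional, if a mechanism claim is to be kept and the timetable still allows it.** Give the IPSBQ block to both arms once during delivery, for example at the May 2024 point, when Table 5 already shows coordinator contact with both arms. Take recommendations recorded after that wave as the outcome. Adjust for baseline barriers, baseline behaviour, and recommendations recorded between March and the wave. This assumes that the tracked recommendations can be split by date, which the protocol does not state. The cost is one more survey of up to 20 minutes per participant and an amendment. Unmeasured confounding of barriers and behaviour would remain and should be acknowledged.
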